M9	the 9th month
M12	the 12th month
PPAS	Per-protocol analysis set
PSI	The Parenting Stress Index
SAEs	Serious adverse events
SAP	Statistical analysis plan
SAS	Safety analysis set
SC	Social/communication
SRS	Social Responsiveness Scale
TEAEs	Emergent adverse event
UB	Unusual behaviors
WISC	Wechsler Intelligence Scale

1. Introduction

1.1 Trial information

1.1.1 Background

Autism Spectrum Disorders (ASD) is the most common neurodevelopment dysfunction and disabling disorder in childhood, with a lack of specific clinical treatment methods. Evidence-based study reveals that nutrients supplement can improve the core symptom of ASD. Our previous study demonstrated the children with ASD were found to have lower taurine levels in serum and urine samples. However, whether the taurine supplementation can improve the core symptom of ASD is unclear, and no ASD trial has ever focused on this intervention.

1.1.2 Objective(s)

1.1.1.1 Primary objective

To compare the effect of 3-month taurine supplementation (age-specific doses, 3 times/day) plus behavioral rehabilitation therapy versus placebo plus behavioral rehabilitation therapy on better rehabilitation of ASD core syndrome, reflected by differential age-specific ASD questionnaires evaluation from baseline at month 0 to month 3.

1.1.1.2 Secondary objectives

To compare the effect of taurine supplementation (age-specific doses, 3 times/day) plus behavioral rehabilitation therapy versus placebo plus behavioral rehabilitation therapy on better rehabilitation of ASD core syndrome, reflected by differential age-specific ASD questionnaires evaluation from baseline at 0 month to 6 month, 9month and 12 month-follow-up.

To compare the safety and adherence of taurine supplementation (age-specific doses, 3 times/day) plus behavioral rehabilitation therapy versus placebo plus behavioral rehabilitation therapy.

To compare the effect of taurine supplementation (age-specific doses, 3 times/day) plus behavioral rehabilitation therapy versus placebo plus behavioral rehabilitation therapy on:

- Brain function
- Intestinal flora
- Oxidative stress markers
- Bile acid metabolites

- Taurine concentrations

1.1.3 Endpoints

1.1.1.3 Primary endpoints

The primary endpoints addressing the primary objectives:

Change from baseline at month 0(M0) to month 3(M3) in:

- The Gesell score
- The Wechsler intelligence scale (WISC) score
- The Childhood Autism Rating Scale (CARS) score

Change from baseline at M0 to month 1(M1), month 2(M2), month 3(M3) in:

- The Autism Treatment Evaluation Checklist (ATEC) score
- The Autism Spectrum Rating Scales (ASRS) score
- The Social Responsiveness Scale (SRS) score
- The Identification and Management of Feeding Difficulties (IMFeD) score
- The Six Gastrointestinal Severity Index(6-GSI) score
- The Children's Sleep Habits Questionnaire (CSHQ) score
- The Parenting Stress Index (PSI)

1.1.1.4 Secondary endpoints

The secondary endpoints addressing the secondary objectives:

Change from baseline at M0 to month 6(M6) ,month 9(M9) and month 12(M12) in:

- The Gesell score
- The Wechsler intelligence scale (WISC) score
- The Childhood Autism Rating Scale (CARS) score
- The Autism Treatment Evaluation Checklist (ATEC) score
- The Autism Spectrum Rating Scales (ASRS) score
- The Social Responsiveness Scale (SRS) score
- The Identification and Management of Feeding Difficulties (IMFeD) score
- The Six Gastrointestinal Severity Index(6-GSI) score
- The Children's Sleep Habits Questionnaire (CSHQ) score
- The Parenting Stress Index (PSI)

1.1.1.5 Supportive endpoints

The supportive endpoints addressing the secondary objectives:

Effect endpoints:

Change from baseline at M0 to M3 on:

- Hemoglobin concentration in cortical metabolism
- Intestinal flora
- Serum metabolites level, including:
 - Oxidative stress markers
 - Bile acid metabolites
 - Taurine concentrations

Safety endpoints:

- Number of treatment emergent adverse events (TEAEs) from baseline at M0 to M3
- Number of serious adverse events (SAEs) from baseline at M0 to M3.
- Number of adverse events (AEs) from baseline at M0 to M3.

1.1.4 Type of trial

This is a 3-month intervention with a total of 12-month follow-up, randomized, double-blind, placebo-controlled, two-armed, parallel group, single-center, exploratory trial comparing taurine supplementation (age-specific doses, 3 times/day) with placebo on better rehabilitation of ASD core syndrome in ASD children aged 2-18 years.

2. Statistical considerations

2.1 Sample size determination

Sample size calculation is precluded from this trial due to exploratory design, as well as a lack of literature and data. 60 subjects (30 per group) are expected to meet the regular outpatient workload in the study site, which will be expected to reach the size within a year.

2.2 Definition of analysis sets

- The full analysis set (FAS):
includes all randomized subjects according to the intention-to-treat (ITT) principle, regardless of actual treatment subjects receive. If any subject fails to complete at least one evaluation after randomization, modified ITT will be used as FAS instead.
- The per-protocol analysis set (PPAS):
includes all randomized subjects who receive and complete the randomized intervention during the whole intervention period (i.e. M0 to M3).
- The safety analysis set (SAS):

includes all randomized subjects exposed to at least one dose of randomized treatment. Any observation excluded from the analysis will be documented before database lock with the reason for exclusion provided.

Two observation periods are defined for each subject:

- In-trial: The in-trial period is defined as the uninterrupted time interval from date of randomization to date of last contact with trial site.
- On-treatment: The on-treatment period will therefore be from the date of first trial product administration to date of last trial product administration excluding potential off-treatment time intervals triggered by at least 7-day missed doses.

The in-trial and on-treatment periods define the patient years of observation and patient years of intervention, respectively, as the total time duration in the periods.

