2.3 Statistical analysis

Effect endpoints will be analyzed using the FAS and PPAS; safety endpoints will be analyzed using the SAS.

Results from effect endpoints will generally be accompanied by two-sided 95% confidence intervals(CI) and corresponding p-values. Significant difference will be claimed if two-sided 95% CI lie away from null. Effect size will be evaluated by corresponding Cohen's D values, which are calculated as mean difference between groups divided by standard deviation for each endpoint in corresponding analysis set (details in appendix Table 1).

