2.3.2 Primary endpoints

The primary endpoints are defined as change in scores of ASD-related scales from baseline at M0 to M3.

Descriptive statistics of primary endpoints

Mean and standard deviation of primary endpoints at each visit, and changes of mean and standard deviation from baseline to each visit will be presented.

Primary analysis for primary endpoints

Using unimputed data of primary endpoints in FAS, exploratory mixed-effects models, preferably generalized linear mixed model (GLMM) for repeated measures analysis, in the condition for endpoints of >2 visits. This analysis investigates if there are group-specific differences over time. The maximum likelihood method will be used to estimate the mean difference between the two groups and their 95% CI, with Gaussian distribution and identity link function; baseline score, group (group), time point (visit) and group \times visit interaction as fixed effects. The time point(visit) is treated as categorical variable in the models. Random slope with unstructured covariance will be preferred as priority; if convergence is not able to be achieved, random intercept will be performed as an alternative.

Otherwise, ANCOVA will be performed to estimate the mean difference between the two groups and their 95% CI, with group (group) as independent variable, and baseline score, time point (visit) and group \times visit interaction as covariates for outcomes with only 2 visits available. The available visits are defined as >10 observations at a single visit. The reason for this alternative method is explained in the Change Log.

For imputed data of primary endpoints, multiple imputation will be considered for handling missing outcomes. More details are described in 2.3.4.

Secondary analysis for primary endpoints

● Per-protocol analysis

Using unimputed data of primary endpoints in PPAS, exploratory mixed-effects models, preferably generalized linear mixed model (GLMM) for repeated measures analysis, in the condition for endpoints of >2 visits. Otherwise, ANCOVA will be performed if only 2 visits are available for the scores of ASD-related scales. The statistical method is the same as primary analysis for primary endpoints.

● Covariate-adjusted analysis

Covariate-adjusted analysis for primary endpoints is performed in FAS and PPAS using the same statistical method as primary analysis.

Covariates are baseline values (missing imputed) including:

- Age (years)
- Sex (1,Boy;2,Girl)

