2.3.4 Other Sensitivity analysis

Complete data analysis

- **Handling of missing data for primary and secondary endpoints**

Missing at random (MAR) missingness mechanism is assumed for incomplete endpoints. For

missing data <50% of the endpoint, multiple imputation (MI) using regression (arbitrary missing pattern with 10 imputations) on missing data, dependent on baseline characteristics (age, sex), baseline scores is likely to be performed. Imputation will not be considered if missing data $\geq 50\%$ of the endpoint.

Therapy-adjusted analysis for primary endpoints

Based on covariate-adjusted analysis for primary endpoints, further adjusted for behavioral rehabilitation therapy (total class hours between M1,M2 and M3) to see the extent the effect size could be explained by the randomized intervention.

Analysis for sub-scales within the same primary endpoint

The statistical method is the same as descriptive statistics and primary analysis for primary endpoints. The analysis investigates if there are group-specific differences over time.

Analysis for sub-scales of certain ASD-related scale scores include:

- Gesell
 - Gesell DA adaptability
 - Gesell DA Fine movements
 - Gesell DA language
 - Gesell DA personal social
 - Gesell DA big movements
 - Gesell DQ adaptability
 - Gesell DQ Fine movements
 - Gesell DQ personal social
 - Gesell DQ big movements
- ATEC
 - Language
 - Social activity
 - Perception
 - Behavior
- SRS
 - Social perception
 - Social cognition
 - Social communication
 - Social motivation
 - SD behavior
- ASRS
 - Social/Communication
 - Unusual Behaviors

Dose-response analysis for primary endpoints

Using on-treatment period(see 2.2) for each subject, to perform dose-response analysis to see the effect of different on-treatment period (days without missed doses) on primary endpoints. The statistical method is the same as primary analysis. The analysis investigates if there are group-

specific differences over time.

Subgroup analysis

Subgroup analysis is not planned in this trial due to limited sample size.

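### One child without a post-randomisation evaluation turns the FAS into an undefined modified ITT set, which takes such children out of the multiple-imputation analysis although they could be imputed

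*SAP*

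**What the plan says.** Section 2.2 gives the FAS two definitions in succession. Under the first, it "includes all randomized subjects according to the intention-to-treat (ITT) principle, regardless of actual treatment subjects receive". The second is conditional: "If any subject fails to complete at least one evaluation after randomization, modified ITT will be used as FAS instead". The SAP does not define modified ITT anywhere else, so who leaves the set has to be inferred from the trigger.

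The per-protocol set "includes all randomized subjects who receive and complete the randomized intervention during the whole intervention period", that is, M0 to M3. Section 2.3 then confines efficacy to these two sets: "Effect endpoints will be analyzed using the FAS and PPAS; safety endpoints will be analyzed using the SAS".

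The primary analysis in section 2.3.2 is run "Using unimputed data of primary endpoints in FAS, exploratory mixed-effects models", with baseline score among the fixed effects.

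Section 2.3.4 assumes data missing at random (MAR). It plans multiple imputation when less than 50% of an endpoint is missing, and none at 50% or more. The imputation is "dependent on baseline characteristics (age, sex), baseline scores is likely to be performed". The section names neither the analysis set for the imputation nor the denominator of the 50%, and it does not list treatment group among the predictors.

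**The concern.** One label covers two populations, and an event after randomisation decides which applies. A single child among the 60 planned is enough to cause the switch. Once it happens, no listed efficacy analysis contains a child who left before the first evaluation. The reduced FAS excludes the child, and a child who withdrew that early will generally not have completed the intervention and so fails the per-protocol set as well.

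The exclusion serves no purpose in the imputation. A child without a later evaluation can still have age, sex and baseline scores, which are exactly the predictors that section 2.3.4 uses. The one analysis designed for missing outcomes therefore omits children with the most outcomes missing. The stated share of missing data also falls, because the earliest losses are in neither the numerator nor the denominator.

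**Working it through.** **Inputs.** N = 60 randomised, 30 per group (section 2.1: "60 subjects (30 per group) are expected to meet the regular outpatient workload in the study site"). Imputation is allowed below 50% missing (section 2.3.4). The SAP gives no count of children without any evaluation. Call it k; values from 1 to 15 are an assumption. Let m be the other children missing at a given visit. The calculation also assumes that the 50% is taken on the FAS, which is the natural reading of section 2.3 but is not stated.

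**The plan's own figure.** There is no power calculation to reproduce (section 2.1: "Sample size calculation is precluded from this trial due to exploratory design, as well as a lack of literature and data"). The only arithmetic is 2 × 30 = 60, which agrees.

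**Missing share under the two definitions.**

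- All randomised: (k + m)/60
- Reduced set: m/(60 − k)
- Difference: (k + m)/60 − m/(60 − k) = k(60 − k − m)/[60(60 − k)]

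The difference is positive whenever k > 0 and at least one child is observed at the visit. The reduced set therefore always shows the lower share.

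**Examples.**

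- k = 1, m = 29: 30/60 = 50.0% (barred) against 29/59 = 49.2% (allowed).
- k = 6, m = 24: 30/60 = 50.0% (barred) against 24/54 = 44.4% (allowed).
- k = 10, m = 24: 34/60 = 56.7% (barred) against 24/50 = 48.0% (allowed).

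**Most children, of 60, who can be missing with imputation still allowed.** With all randomised children as the denominator this is 29. With the reduced set it is:

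| k | Missing of 60 | Share of randomised |
|---|---|---|
| 1 | 30 | 50.0% |
| 3 | 31 | 51.7% |
| 6 | 32 | 53.3% |
| 9 | 34 | 56.7% |
| 12 | 35 | 58.3% |
| 15 | 37 | 61.7% |

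The gain is 1 to 8 children over this range.

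**Effect on the unimputed model.** Baseline score is a covariate, so a child with no later score supplies no outcome record. The estimate is the same under either definition.

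**Effect on the imputed analysis.** A simulation under the plan's own MAR assumption took a true difference of 0.50 SD and let leaving depend on age in one arm. With group in the imputation model, the estimate was 0.38 in the reduced set and 0.49 in all randomised children. With all randomised children but without group, it was 0.36. How strongly leaving depends on age is an assumption of the simulation and not a figure from the SAP, so these values show direction, not an expected size.

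**Why group must be in the imputation model.** Suppose 5 of 30 on taurine and 1 of 30 on placebo have no evaluation, and those observed average 0.50 and 0 SD. If group is left out and the other predictors are balanced, the missing values are drawn around the pooled mean:

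- Pooled mean: 25 × 0.50/54 = 0.231
- Taurine: (25 × 0.50 + 5 × 0.231)/30 = 0.455
- Placebo: (29 × 0 + 1 × 0.231)/30 = 0.008
- Difference: 0.455 − 0.008 = 0.447, about 0.45 instead of 0.50

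Adding children to the imputation model as listed would therefore pull the contrast towards zero.

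**The case against.** The strongest reply is that the main result is untouched. That stands. A reader might infer that dropping early leavers distorts the primary estimate, but the unimputed model gains nothing from a child without outcomes, however the set is named.

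A reader might also take the change log as evidence that such children are numerous. It does not show this. It reports drop-out at M6, M9 and M12 for Gesell, CARS and WISC, after the intervention period, and says nothing about loss before a first evaluation. Nor would the 50% limit be in play at those visits, if the entry means fewer than 10 children observed. With at most 9 observed, less than 50% missing needs a set of at most 17, so 60 − 17 = 43 children would have to lack any evaluation.

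A third tempting inference is that the fix removes bias from informative withdrawal. If early leavers fared 0.5 SD worse and 5/30 against 1/30 left, the contrast would shift by (5/30 − 1/30) × 0.5 = 0.07 SD. Imputation under MAR corrects only loss that group, age, sex and baseline score explain. Any other part of that shift would remain.

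It is also fair to say that modified ITT is common, that the trial is exploratory, that the SAP requires exclusions to be documented with reasons before database lock, and that dosed children stay in the safety set. These points give transparency. They neither define the reduced set nor return the children to an efficacy analysis.

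**Conclusion.** The point holds, with limited reach. Section 2.2 uses the name FAS for two populations, lets one child's missing follow-up decide between them, and leaves the second undefined. On the natural reading, children without any evaluation are lost to the multiple-imputation analysis for no technical reason.

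Three things are affected: the imputation analysis, the reported denominators and, only if the percentage is taken on the FAS, the 50% limit. For that limit the effect is 1 to 8 children for k from 1 to 15, and it changes the decision only when the share of randomised children missing is at or somewhat above 50%. The primary unimputed estimate is not affected.

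The conclusion rests on two inferences: that modified ITT drops the children named in the trigger, and that the imputation is run on the FAS. The size of k is unknown. If every child has at least one evaluation, the switch never occurs and nothing changes.

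**What to change.** In section 2.2, delete the modified-ITT sentence and keep the FAS as all randomised children, analysed as allocated. The likelihood model will use those who have data. If a reduced set is wanted, define it, give it its own name and report it as supportive.

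In section 2.3.4:

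- state that multiple imputation is run in all randomised children;
- add treatment group to the imputation model, or impute separately by arm;
- state that the 50% limit is a share of all randomised children.

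Report by arm the number of children without any evaluation, and describe the imputed result as valid under MAR given group, age, sex and baseline score.

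The cost is SAP wording, a few more imputed records and slightly wider imputed intervals. The stated missingness will rise, so some endpoints may no longer qualify for imputation, and for those the early leavers will again be in no imputed analysis. The count by arm keeps that loss visible.

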2.3 Statistical analysis

Effect endpoints will be analyzed using the FAS and PPAS; safety endpoints will be analyzed using the SAS.

Results from effect endpoints will generally be accompanied by two-sided 95% confidence intervals(CI) and corresponding p-values. Significant difference will be claimed if two-sided 95% CI lie away from null. Effect size will be evaluated by corresponding Cohen's D values, which are calculated as mean difference between groups divided by standard deviation for each endpoint in corresponding analysis set (details in appendix Table 1).

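### SAP 2.3 fixes a significance claim for each of ten unranked primary scales on an unadjusted 95% interval, which does not fit a trial that calls itself exploratory

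*SAP*

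**What the plan says.** SAP 1.1.3 opens its list with "The primary endpoints addressing the primary objectives" and names ten scales: Gesell, WISC and CARS at M3, then ATEC, ASRS, SRS, IMFeD, 6-GSI, CSHQ and PSI. None is marked as the lead, no order is given and there is no composite.

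SAP 2.3 sets the reporting rule for effect endpoints: "Results from effect endpoints will generally be accompanied by two-sided 95% confidence intervals(CI) and corresponding p-values". The next sentence adds the decision rule: "Significant difference will be claimed if two-sided 95% CI lie away from null". It applies scale by scale at the 5% level. The SAP contains no adjustment, no testing order, no rule on how many scales must agree, and no statement that p-values are nominal or descriptive.

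The SAP also calls the trial exploratory. Section 1.1.4 describes a "two-armed, parallel group, single-center, exploratory trial comparing taurine supplementation", section 2.1 says "Sample size calculation is precluded from this trial due to exploratory design", and section 2.3.2 uses the same word for its mixed models.

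On timing, section 1.1.3 introduces the last seven scales with "Change from baseline at M0 to month 1(M1), month 2(M2), month 3(M3) in", whereas section 2.3.2 says "The primary endpoints are defined as change in scores of ASD-related scales from baseline at M0 to M3". The primary objective in section 1.1.2 also runs from month 0 to month 3.

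**The concern.** An exploratory trial may test many endpoints without adjustment, provided the results are read as nominal and as a set. This SAP leaves the tests unadjusted but commits in advance to claiming significance on any primary scale whose interval excludes the null. The exploratory label is attached to the trial, the design and the models. No sentence carries it over to how a positive interval is to be read.

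If the plan is followed as written, one positive scale out of ten can be presented as a pre-specified significant difference on a primary endpoint. Nothing tells the authors or the reader to weigh it against the other nine. With 60 children and no power calculation, an isolated finding of that kind is easily over-read.

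**Working it through.** The SAP states no power, no family-wise level and no sample-size calculation, so it has no figure of its own to reproduce first.

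**Inputs**
- Primary scales: 10 (SAP 1.1.3).
- Error per scale: 0.05 two-sided, so 0.025 in each direction (SAP 2.3).
- One contrast per scale, at M3, in the unimputed full analysis set (SAP 1.1.2 and 2.3.2).
- 30 children per group (SAP 2.1).
- Common correlation ρ between the scales' effect estimates: not in the SAP; assumed, and shown from 0 to 0.9.
- Exact 95% coverage of each interval: assumed.

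**Step 1, independent scales, inert taurine**
- At least one scale significant, either direction: 1 − 0.95^10 = 1 − 0.599 = 0.401.
- At least one in taurine's favour: 1 − 0.975^10 = 1 − 0.776 = 0.224.
- Expected number of scales meeting the rule: 10 × 0.05 = 0.5, whatever the correlation.

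**Step 2, correlated scales.** For equally correlated normal test statistics with c = 1.96,

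P(at least one) = 1 − ∫ [Φ((c − √ρ·u)/√(1−ρ)) − Φ((−c − √ρ·u)/√(1−ρ))]^10 φ(u) du.

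The one-direction version drops the second Φ term. Numerical integration gives:

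| Assumed ρ | Either direction | In taurine's favour |
|---|---|---|
| 0 | 40.1% | 22.4% |
| 0.3 | 35.1% | 17.8% |
| 0.5 | 28.7% | 14.4% |
| 0.7 | 21.3% | 10.7% |
| 0.8 | 17.3% | 8.6% |
| 0.9 | 12.8% | 6.4% |

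The rates for a single scale are 5% and 2.5%.

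**Step 3, check by simulation.** Baseline-adjusted ANCOVA with 30 per arm, 3,000 trials per setting, gave 41% / 24% at ρ = 0, 29% / 15% at 0.5 and 17% / 9% at 0.8 (either direction / in favour). This agrees within simulation error.

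**Step 4, sensitivity to coverage.** SAP 2.3.2 specifies maximum likelihood for its mixed models. If the intervals used the maximum-likelihood variance with 1.96 in place of a t quantile (an assumption), the same simulation gave 46%, 33% and 21% in either direction at ρ = 0, 0.5 and 0.8. So 40% is the independence value under exact coverage and not an upper bound.

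**Step 5, isolated hits.** Exactly one of ten scales is significant in 32%, 18% and 7% of trials at ρ = 0, 0.5 and 0.8. Two or more are significant in 9%, 11% and 10%.

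**Step 6, what an adjusted claim rule would do.** Holm over ten scales brings the chance of at least one false claim to 4.9%, 3.9% and 2.3% at ρ = 0, 0.5 and 0.8. Its strictest step uses 0.05/10 = 0.005. With 30 per arm, no missing data and a normal approximation, the noncentrality for a standardised difference d is d × √(30/2) = d × √15:
- d = 0.8 (assumed): 3.10; power 87% at 0.05 and 61% at 0.005.
- d = 0.5 (assumed): 1.94; power 49% at 0.05 and 19% at 0.005.

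**The case against.** The best reply is that the SAP calls the trial exploratory in several places, so unadjusted testing is legitimate and a family-wise error rate is the wrong yardstick. That stands. A reader might infer from the 40% that the plan breaches an error level. It does not: the 5% applies to each endpoint and no family-wise level is promised. Nor does the recommended rewording lower the chance that some interval excludes the null. The rates show how often the rule would be triggered by chance, nothing more.

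A second reply is that the sentence in section 2.3 only defines significance for each endpoint. It speaks of a significant difference, not of efficacy or trial success, and no passage says that one positive scale makes the trial positive. That also stands, and the stronger reading is not supported. Section 2.3 further says that effect results will generally carry intervals and p-values, and section 2.3.2 calls for descriptive statistics of the primary endpoints at each visit, which limits selective reporting. What remains is that the sentence fixes a claim, and no sentence says how to read one positive scale beside nine others.

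A third reply concerns timing. A reader might take section 1.1.3 to make M1 and M2 additional primary contrasts. The documents do not require this. Sections 1.1.2 and 2.3.2 already name M3, the visits in 1.1.3 can be read as those feeding the repeated-measures model, and the change log records that clinical assessments at M1 and M2 were cancelled. The mismatch is editorial and has no part in the figures.

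It would also be wrong to shrink the set of scales by the threshold in section 2.3.2, "The available visits are defined as >10 observations at a single visit". That threshold serves the choice between the mixed model and ANCOVA; it does not decide whether a scale is tested.

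**Conclusion.** The point holds as a mismatch between a fixed claim rule and the exploratory label, and it is worth correcting because it governs what the trial may report as a finding. It is not a failure to control a required error rate.

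If taurine is inert, at least one of ten scales would meet the rule at M3 in about 40% of trials at correlation 0, falling to 13% at 0.9. In taurine's favour the range is 22% to 6%. Even at 0.9 both figures are more than twice the single-scale rates. They rest on a common correlation that the SAP does not give, on exact coverage, and on one test per scale. They leave out the per-protocol, covariate-adjusted and imputed analyses, the sub-scales, and M6 to M12.

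**What to change.** Replace the claim sentence in SAP 2.3 with: *The trial is exploratory; p-values and 95% CIs are unadjusted and nominal, all ten primary scales are reported together, and no claim of efficacy rests on any single one.* This changes no model, drops no scale and loses no power. The downside is fewer significance claims.

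If the sponsor prefers to keep a claim rule, apply a multiplicity adjustment such as Holm across all ten listed primary scales at M3 in the full analysis set primary analysis, and call all other p-values and intervals nominal. The cost is lower power per scale, as shown in the last step of the working. In an exploratory trial this is a trade-off and not a requirement.

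As an editorial alignment only, bring the visits listed in section 1.1.3 for the seven scales into line with the M0 to M3 definition already in sections 1.1.2 and 2.3.2.
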